analytical methods	
 
* Description of transmission dynamics: rolling incidence rate of COVID-19 disease throughout one year, adjusting for the sensitivity of SARS-CoV-2 RT-PCR on nasal swabs by delay between symptom onset and testing; SARS-CoV-2 infection incidence rate, SARS-CoV-2 annual attack rate, secondary infection rate, and infection fatality risk by age group, by adjusting for the proportion asymptomatics.
 
* Risk factor analysis for SARS-CoV-2 infection and COVID-19 disease, and for severity (hospitalisation), overall and following household transmission in particular.
 
* Model basic and effective reproductive numbers (<math>R_0</math> and <math>R_e</math>), generation time distribution, ratio of transmissibility between symptomatic and asymptomatic cases, duration of the infectious period, household secondary infection rate.
 
* Explore the correlation between <math>R_0</math> and <math>R_e</math>, and the uptake of measures to reduce exposure/ transmission.
 
* Case-cohort, case- control or similar analysis to estimate vaccine effectiveness against confirmed COVID-19 in the population-based surveillance and cohort analysis to estimate vaccine effectiveness against SARS-CoV-2 seroconversion (among sero-survey participants)
 

safety	
The study does not involve an investigational product or intervention

statistical methods	Descriptive (probabilistic) and inferential statistics Negative binomial regression for risk factor analysis Development of a compartmental mathematical model to describe the spread of SARS-CoV-2 on the population level
---------------------	---

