### 3. Study Design

Prospective cohort study (observational). We will use the established HDSS to set up population-based COVID-19 surveillance in a household cohort. From any individual in this population reporting any respiratory sign (symptom or lowered peripheral oxygen saturation) or loss of smell or taste, with or without fever, we will collect a respiratory specimen and test these for SARS-CoV-2 virus by PCR, during 12 months. These cases will be identified through bi-weekly household visits, through an alert system involving community leaders and HDSS interviewers, or when presenting with symptoms at healthcare centres or at the referral hospital. Identified healthcare facilities will then alert the study team if a possible case from the HDSS population is consulted or admitted, if the patient agrees. Demographic, epidemiological and clinical data (comorbidities, medication, obesity, HIV, TB, smoking) of possible cases and of the source population will be recorded at baseline; recent illness, potential risk exposure of each household member (including duration and type) to SARS-CoV-2 positive individuals, uptake of measures to reduce exposure/transmission, and barriers to the uptake of such measures, will be

recorded/updated during every household visit. COVID-19 vaccination status will be recorded from possible cases and compared to that of a subset of the population, in a case-cohort design to determine vaccine effectiveness against symptomatic COVID-19.

An age-stratified serial sero-survey will be conducted at baseline in a subset of the population in the population-based COVID-19 surveillance, and at 3, 6 and 12 months, after confirmation of community transmission. Recording vaccination status of all sero-survey participants, we will determine vaccine effectiveness against SARS-CoV-2 seroconversion in a cohort design.

Household transmission will be specifically investigated, by investigating contact history, vaccination status, and the presence of SARS-CoV-2 virus and serology among household members twice during the month after the symptom onset of a household index case.

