## 4. Participants, Population & Selection

### 4.1 Setting

Polana Caniço, peri-urban Maputo, Mozambique: a health- and demographic surveillance system (HDSS) covering a population of 15,393, in the catchment area of the Polana Caniço General Hospital (PCGH), one out of two COVID-19 referral facilities in Maputo.

The population in peri-urban Polana Caniço is relatively representative of the increasingly urban population in Southern Africa, having young and mobile inhabitants. Moreover, the population suffers increasingly from non-communicable diseases, and prevalence of HIV and active tuberculosis is presumed to be important. Research gaps on COVID-19 transmission dynamics include whether the reproduction number could be different in such different (eg. younger) population. Also, the potential association between (uncontrolled) HIV infection or (active) tuberculosis and COVID-19 infection and severe disease, needs to be elucidated.

The Polana Caniço-HDSS has been established since 2017. In total, as of time of writing, 2108 households (defined as residents of the same building, sharing a cooking area) have been enrolled in the HDSS. All members residing in the household for at least 3 months (infants, children, adults, elderly) are enrolled in the HDSS. Surveillance rounds are currently carried out six-monthly. Demographic and health indicators collected in each surveillance round include but are not limited to: fertility/birth rate, mortality/cause of death, migration, disease cases, trauma and violence, socioeconomic status, water and sanitation facilities, risk factors for the acquisition of chronic diseases, women's health and family planning, immunization, risk behaviours and cultural practices related to the transmission of STI (including HIV and syphilis). Testing for HIV and syphilis is planned to be added as part of the surveillance rounds, from October 2020 onwards. Data on births, deaths, internal and external migration, pregnancies and their outcomes, and any other relevant events from a demographic perspective, are continuously reported by community key informants and confirmed through home visits.

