An **age-stratified random sample** of that population will be selected for the **repeated sero- and social mixing survey**. By age stratum (0-17 years; 18-50 years; >50 years) we randomly select 800 individuals (simple random sample per age stratum; 2400 in total) from the Polana Caniço HDSS population (regardless of infection or disease status or history), from whom during home visits dried blood spots will repeatedly be collected at 0, 3, 6 and 12 months, vaccination status against COVID-19 will be recorded, and who will be asked to respond to a social mixing questionnaire. A HDSS sampling frame of all individual participants in the HDSS with socio-demographic data and unique identifiers, is available, and will be used to select a simple random sample of individuals by age group.

When a member of a household with no prior widespread transmission (see exclusion criteria) tests SARS-CoV-2 positive, we will revisit the household twice for a household transmission investigation: as soon as possible after the result of the household index case (baseline), and once again one month after symptom onset of the household index case. An initial contact report form will be filled in as soon as possible, ideally within 24 hours, after laboratory confirmation of the primary case in the household. Respiratory and dried blood spot samples will be collected of everyone considered resident (as defined by the HDSS) in the household and who has been in contact with the SARS-CoV-2 positive individual, regardless of age and presence or absence of symptoms. Respiratory samples will be analysed by RT-PCR for SARS-CoV-2 to assess presence of virus and viral load. The dried blood spots for serology on the Luminex assay. Data will be collected on household exposures of contacts and vaccine receipt. Symptomatic household contacts will be tested whenever symptoms appear, as part of the population-based surveillance. This is planned for upto 100 household index cases.

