## 7. Statistical Analyses

### 7.1 Methods

All estimated transmission or clinical outcome indicators will be adjusted for the design effect, related to the selection of HDSS enumeration areas (clusters) within the source populations. Intraclass correlation coefficients can be deducted from previous studies in the HDSS. The results of the sero-survey and social mixing survey will additionally be adjusted for age-stratified sampling.

We will calculate a incidence rate of COVID-19 disease throughout one year, adjusting for the sensitivity of SARS-CoV-2 RT-PCR on nasal swabs by delay between symptom onset and testing. Using the longitudinal sero-survey data, determining the proportion of asymptomatics, we will be able to adjust the clinical incidence rate to a SARS-CoV-2 infection incidence rate, and determine the SARS-CoV-2 infection annual attack rate and the infection fatality risk by age group.

We will undertake three risk factor analyses: of SARS-CoV-2 infection, of COVID-19 disease (symptomatic infection), and of COVID-19 hospitalisation and death (severe disease). Using negative binomial regression, we will investigate the association with socio-demographic factors, clinical characteristics such as underlying medical conditions, and uptake of preventive measures. We also investigate the association between SARS-CoV-2 infection (from the sero-survey) and recent exposure, contact and mobility patterns (from the social mixing questionnaire).

We will assume everyone will be susceptible initially and basic and effective reproductive numbers ( $R_0$  and  $R_e$ ) will be calculated by the rate of change of incidence over successive serial intervals (time between onset of infection of index and onset of infection of infected).

We will use established methods (Cauchemez et al 2004; te Beest et al 2013) to estimate generation time distribution, ratio of transmissibility between symptomatic and asymptomatic cases, duration of

the infectious period, and the basic reproduction number, from the transmission data collected in households.

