We will derive brand-specific total vaccine effectiveness against infection and against disease, in respectively a case-cohort design and a cohort design. Total vaccine effectiveness is the protection of vaccinees due to direct effects and added protection of vaccinees owing to vaccination of their neighbors or contacts, while overall vaccine effectiveness considers protection of an entire population, irrespective of the vaccination status of its individual members, due to the combination of total protection and protection of non-vaccinees due to vaccination of their neighbors or contacts (Ali et al 2015). To derive total vaccine effectiveness against infection, we will compare the proportion of sero-survey participants who seroconverted in the past 3 months among vaccinated against the proportion in non-vaccinated, adjusting for age and sex and other confounders. To derive total vaccine effectiveness against disease, we will compare the odds of vaccination among symptomatic confirmed SARS-CoV-2 cases detected through the population-based surveillance with the odds of vaccination among sero-survey participants who did not seroconvert in the past 3 months, in a case-cohort design. We will also explore overall vaccine effectiveness against disease using regression models comparing housing blocks with different levels of vaccination coverage among sero-survey participants.

We will estimate the conventional data-based secondary attack rate, which is the proportion of seroconversion among identified household contacts. However, these are not necessarily all secondary infections from the household index case, and could be tertiary. Therefore we will also derive a model-based secondary attack rate, estimating the number of actual secondary infections of the household index case. To do so, we could use a chain-binomial statistical model, as described by Jing et al (doi:10.1016/S1473-3099(20)30471-0), with an expectation-maximisation algorithm to account for (a) uncertainty in the infection time of asymptomatic infections, for (b) an incubation and infectious period distribution, as described in literature, and consider (c) the timing of symptom onset in

symptomatic household contacts and (d) the age-specific proportion of asymptomatic infections as estimated from the active population-based surveillance and sero-survey.

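### Section 7.1 adjusts vaccine effectiveness against infection for age, sex and confounders but names no adjustment for effectiveness against disease, leaving it open to confounding by age

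*Combined protocol and SAP*

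**What the plan says.** Section 7.1 defines two contrasts in adjacent sentences. VE against infection compares the proportions who seroconverted among vaccinated and unvaccinated sero-survey participants, "adjusting for age and sex and other confounders".

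For disease the text is: "To derive total vaccine effectiveness against disease, we will compare the odds of vaccination among symptomatic confirmed SARS-CoV-2 cases" found by the population-based surveillance, "with the odds of vaccination among sero-survey participants who did not seroconvert in the past 3 months, in a case-cohort design". No covariate, matching, stratification or model is named.

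The other places that describe this analysis add none. Section 3 says vaccination status of cases will be compared with that of a population subset, "in a case-cohort design to determine vaccine effectiveness against symptomatic COVID-19". The Synopsis leaves the design open: "Case-cohort, case- control or similar analysis to estimate vaccine effectiveness against confirmed COVID-19 in the population-based surveillance". Table 1 only lists the outcome.

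The comparator comes from the sero-survey, for which section 4.2 says, by age stratum, "we randomly select 800 individuals (simple random sample per age stratum; 2400 in total"; the strata are 0-17, 18-50 and over 50 years. The cases come from the whole HDSS population. A general sentence early in 7.1 reads: "The results of the sero-survey and social mixing survey will additionally be adjusted for age-stratified sampling".

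**The concern.** The disease contrast sets cases from one source against comparators from another. If vaccination is more common at some ages, and symptomatic disease is too, an unadjusted odds ratio mixes the effect of the vaccine with the age pattern of roll-out and illness. The same applies to sex and to the medical conditions recorded at baseline.

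Adjusting for sampling is a different operation from adjusting for confounding. Weighting the comparator makes it represent the HDSS population; it does not make cases and comparators alike in age. It is also unclear whether the sampling sentence, written for sero-survey results, covers a contrast whose case side comes from surveillance.

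Brand-specific VE against PCR-confirmed clinical infection is a listed secondary objective in section 2. Followed as written, the plan would report an adjusted VE against infection beside an unadjusted VE against disease, which adds an avoidable reason for the two to differ.

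**Working it through.** Section 7.2 gives no sample size, power or precision for VE against disease, so there is no stated figure to reproduce. Its 66% and 97% power figures concern seroconversion and are not at issue.

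**Inputs from the documents.** The comparator sample is one third per age stratum (800 of 2400, section 4.2). Coverage is 20% among the 2400, and the anticipated VE is 50% (section 7.2, stated for the seroconversion contrast).

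**Assumptions.** VE is the same at every age, nothing but age differs between cases and comparators, and the removal of seroconverters from the comparator is ignored. The age-specific values below are also assumed.

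**Illustration 1: children and adults.** Coverage is 0% under 18 and 30% in adults, which gives 2/3 × 0.30 = 20% across the sample. Let k be the children's share of the cases that would occur without vaccination.

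- Odds of vaccination in cases = (1 − k) × 0.30 × (1 − VE) / [(1 − k) × 0.70 + k]
- Unadjusted VE = 1 − (odds in cases / odds in comparator)
- Case odds at k = 0.10 and true VE = 0.50: 0.135 / 0.730 = 0.185
- Comparator unweighted: 0.20 / 0.80 = 0.250, so unadjusted VE = 1 − 0.185/0.250 = 26%
- Comparator weighted to a population with 45% children: coverage 0.55 × 0.30 = 0.165, odds 0.165 / 0.835 = 0.198, so unadjusted VE = 1 − 0.1849/0.1976 = 6%

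Here k is not the share among the cases actually observed. Vaccination removes adult cases, so the observed share of children is 0.10 / (0.10 + 0.63 + 0.135) = 11.6%.

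If instead k = 0.45, the case odds are 0.0825 / 0.835 = 0.0988. Unadjusted VE is then 60% unweighted and 50% weighted, the latter because the age mix of the cases absent vaccination equals that of the assumed population.

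**Illustration 2: three strata.** Coverage is 0/20/40% and true VE 50%, with ages in the order 0-17, 18-50, over 50. The population is 45/45/10%, so the weighted comparator has coverage 0.45 × 0.20 + 0.10 × 0.40 = 13% and odds 0.13/0.87 = 0.149. The unweighted comparator has coverage 20% and odds 0.250.

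| Symptomatic risk by age | Odds in cases | VE, unweighted | VE, weighted |
|---|---|---|---|
| Equal | 0.065/0.870 = 0.075 | 70% | 50% |
| 10/20/30% | 0.015/0.135 = 0.111 | 56% | 26% |
| 25/20/15% | 0.012/0.1935 = 0.062 | 75% | 58% |

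Weighting removes the bias when risk is equal across ages and leaves bias when it is not. In the second row it moves the estimate further from 50%. If the three population strata are equal in size, weighting changes nothing: VE reads 27% with rising risk and 60% with falling risk.

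**Two checks.**

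- With 20% coverage at every age, case odds are 0.20 × 0.5 / 0.80 = 0.125 against 0.250, so VE = 50% whatever the age mix. There is no age bias.
- Within a stratum that has any vaccination, the true value returns. At 18-50 years: 1 − 0.125/0.250 = 50%. Over 50: 1 − (0.20/0.60)/(0.40/0.60) = 50%.

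**The case against.** **Silence is not a decision.** A reader might infer that the sponsor has chosen a crude analysis for disease. The documents do not say so. No section calls this contrast crude or unadjusted, the Synopsis leaves the method open, and the paragraph is loosely drafted: its first sentence assigns the case-cohort and cohort designs to infection and disease in the reverse of what follows. This stands as a caution about intent. It does not supply the missing adjustment.

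**Covariate modelling of disease is planned elsewhere.** Section 7.1 includes negative binomial regressions of COVID-19 disease on socio-demographic factors, medical conditions and preventive measures. These are separate risk-factor analyses, and the VE text does not draw on them.

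**The equal allocation across strata can be corrected.** A reader might infer that drawing 800 per stratum by itself biases the result. If the sampling sentence applies to this contrast, that part disappears. It may also be small: section 7.2 calls the strata comparable in size, which could describe either the samples or the population, whereas section 4.1 describes the setting as "having young and mobile inhabitants". What remains in either case is confounding.

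**Age variation in disease is not asserted.** The plan will estimate the asymptomatic proportion by age group, and its household model uses an age-specific proportion. That allows for a difference without predicting one. The objection stands, and the point is therefore conditional.

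**The two VEs already differ** in endpoint and effect measure, so adjustment is not the only bar to comparing them. This also stands.

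**Conclusion.** The omission is in the text: adjustment is written for VE against infection and for nothing in VE against disease, and no other section fills the gap. Followed as written, the disease estimate is confounded by age whenever coverage and symptomatic risk both vary with age, with or without sampling weights.

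It would be too strong to say that the estimate will be biased, or in which direction. The documents give no age-specific coverage, HDSS age distribution or age-specific case risk, and equal coverage across ages would mean no age bias. The 26% and 6% against a true 50% show what plausible inputs could do; they are not predictions for this study.

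VE is a secondary objective that depends on vaccine introduction, and the remedy costs almost nothing. This is a free or cheap improvement.

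**What to change.** In section 7.1, state that VE against disease will be estimated by a regression, for example logistic, of case status on vaccination. It should adjust for age (more finely than the three sampling strata), for sex, and for the same baseline confounders as VE against infection. State also that sampling weights by age stratum are used for the comparator, so that it is clear how the general sampling sentence applies to this contrast.

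The data are already planned. Section 3 records demographic and clinical data for possible cases and the source population at baseline, and sections 3 and 4.2 record vaccination status for cases and sero-survey participants. A mandatory restriction by date of vaccine eligibility is not needed for this point, and it would require roll-out dates that the plan does not say it collects.

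Cost: SAP wording and a slightly wider interval.

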	
 
Understand non-SARS-CoV-2 etiologies of respiratory disease in the study population
 
Identify factors associated with household SARS-CoV-2 infection and with household infection resulting in Covid19 disease, including viral load and symptoms of household index case, household and individual characteristics and behaviour to prevent infection.
 
Estimate total (of vaccinees) and overall (including indirect protection of non-vaccinated) vaccine effectiveness among the study population, once one or more vaccines are introduced
 

screening, recruitment & randomization	
All household members will be screened for symptoms during biweekly household visits.
 
Individuals reporting any respiratory sign, or loss of smell or taste, with or without fever (either presenting at the COVID-19 care facility or identified through the biweekly household visits) will provide specimens that will undergo PCR testing. Symptoms, clinical outcome, vaccination status against COVID-19, and potential exposure will be recorded.
 
Three age-stratified subsets of the population (0-17 years; 18-50 years; >50 years) will be recruited for a sero-survey at 0, 3, 6 and 12 months and a social mixing survey, repeated 4 times during the outbreak.
 
Household contacts of household cases testing positive for SARS-CoV-2 will be screened for virus and antibodies and for illness 1 day after confirmation of the household index case and 28 days after index case symptom onset

follow-up	
The clinical outcome of individuals with a confirmed SARS-CoV-2 infection (mild cases at home; hospitalised cases in the hospital or after discharge) will be recorded during the weekly visits and at 28 and 56 days post symptom onset.

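### The two vaccine-effectiveness contrasts labelled total estimate approximately direct effectiveness; the 3-month seroconversion window does not exist at month 12, and one sentence swaps the two designs

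*Combined protocol and SAP*

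**What the plan says.** The Synopsis lists as a secondary objective: "Estimate total (of vaccinees) and overall (including indirect protection of non-vaccinated) vaccine effectiveness among the study population". Section 2 repeats total, brand-specific VE among vaccinees for both PCR-confirmed clinical infection and seroconversion. Table 1 lists total VE under the sero-survey, and Section 7.2 computes power for an anticipated crude total VE of 50%.

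Section 7.1 gives the definition: "Total vaccine effectiveness is the protection of vaccinees due to direct effects and added protection of vaccinees owing to vaccination of their neighbors or contacts". It introduces the two analyses, infection first and disease second, as being made "in respectively a case-cohort design and a cohort design". For infection, it will "compare the proportion of sero-survey participants who seroconverted in the past 3 months among vaccinated against the proportion in non-vaccinated", with adjustment for age, sex and other confounders. For disease, it compares the odds of vaccination in symptomatic confirmed cases "with the odds of vaccination among sero-survey participants who did not seroconvert in the past 3 months, in a case-cohort design". The only comparison across different levels of coverage serves another measure: "We will also explore overall vaccine effectiveness against disease using regression models comparing housing blocks with different levels of vaccination coverage".

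The Synopsis describes the designs as "Case-cohort, case- control or similar analysis to estimate vaccine effectiveness against confirmed COVID-19" and "cohort analysis to estimate vaccine effectiveness against SARS-CoV-2 seroconversion (among sero-survey participants"). Section 3 likewise assigns the case-cohort design to symptomatic disease and the cohort design to seroconversion. Sections 4.2 and 5.1 place the sero-survey rounds at months 0, 3, 6 and 12.

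**The concern.** Three things in the VE paragraphs of Section 7.1 do not fit together.

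- **Estimand.** The indirect part of total VE can be seen only against people with less vaccination around them. The unvaccinated participants here live in the same population as the vaccinated and share whatever indirect protection exists. A reader who takes the definition at its word would credit the estimate with herd protection that it does not contain.
- **Window.** The same 3-month window defines the infection outcome and selects the disease comparator. With no blood taken at month 9, neither analysis has a usable definition at the final round.
- **Design labels.** Taken literally, the introductory sentence assigns each design to the wrong outcome.

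**Working it through.** **The plan's own figure.** Section 7.2 takes 2400 participants, 20% coverage (480 vaccinated, 1920 unvaccinated), VE of 50% and seroconversion of 5% over 3 months or 10% over 6 months, and states 66% and 97% power. Reading 5% and 10% as risks in the unvaccinated, a two-sided 5% Fisher exact test gives 67.7% and 95.6%, within 2 points of both. The power figures are not in dispute; only the word total attached to them is.

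**Estimand.** Let r_v and r_u be the risks in vaccinated and unvaccinated people at the coverage actually reached, and r_0 the risk with no vaccination.

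- Planned contrast = 1 − r_v/r_u
- Total VE as defined = 1 − r_v/r_0

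The two differ by r_v/r_u − r_v/r_0, which is zero or positive when r_u ≤ r_0. If indirect protection cuts both groups' risk by a fraction i and direct VE is 50%, the contrast stays at 50% while total VE is 1 − 0.5(1 − i). That is 55%, 60% and 65% for assumed i of 10%, 20% and 30%.

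An illustrative final-size model shows how far the gap depends on inputs. It assumes homogeneous mixing, a leaky vaccine with 50% direct VE and 20% coverage given before the epidemic. With Z the overall attack rate and z_0 the attack rate without vaccination:

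- z_0 = 1 − exp(−R0·z_0)
- Z = 0.8[1 − exp(−R0·Z)] + 0.2[1 − exp(−0.5·R0·Z)]
- r_u = 1 − exp(−R0·Z); r_v = 1 − exp(−0.5·R0·Z); r_0 = z_0

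| Input | Source | Contrast | Total | Gap (points) |
|---|---|---|---|---|
| z_0 = 40% (R0 = 1.28) | Section 7.2 | 46.2% | 64.9% | 18.7 |
| R0 = 2.0 | Section 1.1 | 33.0% | 36.4% | 3.4 |
| R0 = 2.5 | within the Section 1.1 range | 26.2% | 27.8% | 1.6 |
| R0 = 3.4 | Section 1.1 | 17.2% | 17.7% | 0.5 |

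The sign is the same throughout, but the size is not determined by the documents. Vaccination during the epidemic, which is what the plan expects, would change it again.

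**Window.** The intervals between rounds are 3 − 0 = 3, 6 − 3 = 3 and 12 − 6 = 6 months. Table 2, as far as it can be read, marks weeks 1, 13, 25 and 51, which are 12, 12 and 26 weeks apart. Paired samples at months 6 and 12 show that a person converted at some time in six months, not in which half. Section 7.2 computes power for a 6-month risk, but Section 7.1 defines no 6-month outcome.

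**Design labels.**

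| Place | Infection | Disease |
|---|---|---|
| Section 7.1, introductory sentence | case-cohort | cohort |
| Section 7.1, later sentences | comparison of proportions (cohort) | case-cohort |
| Section 3 | cohort | case-cohort |
| Synopsis | cohort | case-cohort, case-control or similar |

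**Minor check, disease comparator.** Section 4.2 samples the sero-survey regardless of infection status, but Section 7.1 drops recent seroconverters from the comparator. Let p be seroconversion in the unvaccinated, and assume a true risk-ratio VE of 50% for both infection and disease. The full sample returns 50%. The restricted one returns 1 − 0.5(1 − p)/(1 − 0.5p):

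- p = 5%: 51.3%
- p = 10%: 52.6%
- p = 20%: 55.6%

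The first two rates are those of Section 7.2. The third is the 6-month share of its 40% annual attack rate if infections are spread evenly.

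**The case against.** The strongest reply is that the gap may be negligible. At the R0 values the protocol itself cites, the model puts the contrast within 3.4 points of total VE, and at 20% coverage there may be little indirect protection to miss. If coverage clusters by housing block, the contrast also picks up some indirect protection. This stands against any claim of a large error. It does not rescue the label, because the design cannot show whether the indirect part is large or small.

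It can also be said that the 3-month window works at months 3 and 6, and that the reversed sentence is corrected by the text after it, so an analyst would not be misled. Both are true. They make these small wording repairs, but the final round still lacks a definition.

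On the comparator, the Synopsis permits a case-control analysis. If the true effect is a hazard ratio of 0.5, the full sample reads 49.4% and 48.7% at 5% and 10% seroconversion and the restricted one 50.6% and 51.3%: equal errors in opposite directions. The choice is therefore one of label rather than accuracy.

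A reader might also infer that vaccine-induced spike antibody will be counted as infection, since the assay in Section 5.4.2 reads both spike and nucleocapsid. The documents do not support that as a finding: they name no vaccine or vaccine antigen. All that can be said is that they state no rule for which antigen defines seroconversion.

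**Conclusion.** Wrong as written, on secondary objectives. The mismatch between definition and contrast, the missing month-12 window and the reversed design sentence all follow from the text alone. The contrasts estimate approximately direct VE, somewhat more if coverage clusters. They lie at or below total VE provided vaccination does not raise the risk of the unvaccinated and confounding is handled.

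Several stronger readings are not supported. No single figure for the gap can be given: about 19 points and about half a point come from the same model with inputs the protocol itself quotes. The effect of the comparator cannot be capped at about 3 points, since it reaches 5.6 at 20% seroconversion; it remains a minor matter of labelling. The household-investigation row of Table 1 also lists total VE, but no contrast is described for it, so it cannot be judged or relabelled on this ground.

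**What to change.** 1. In Section 7.1, in the matching objectives (Synopsis and Section 2), in the sero-survey outcomes of Table 1 and in the VE power statement of Section 7.2, call these contrasts approximately direct VE, and do not report them as including indirect protection. Keep the term total VE for a contrast across coverage levels, such as an exploratory extension of the planned housing-block comparison.
2. Replace the 3-month window, in both the infection outcome and the disease comparator, with seroconversion since the previous sero-survey round, noting that this is 6 months for the last interval.
3. Correct the introductory sentence so that infection has the cohort design and disease the case-cohort design.
4. As a minor point, either use the full sero-survey sample as the disease comparator or keep the restriction and label the result an odds ratio of cases against non-cases.

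The cost is wording only, with no new samples or participants. The plan gives up the claim to total VE from these two contrasts; the block comparison for overall VE stays exploratory, as already planned.
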